### **11.1 Adverse Event Collection in the Case Report Forms**

All adverse events that occur beginning with start of treatment must be captured in the AE Form.

## **12.0 STATISTICAL CONSIDERATIONS**

## **12.1 Data analysis**

Data will be analyzed using an intention to treat principle with patients analyzed in the groups they were randomized to. The primary outcome measure for assessing effectiveness of ZNS (100 mg PO) will be the proportion of officers experiencing PTS 30 days (+/- 3 days) after training in the ZNS group as compared to proportion of officers experiencing PTS in the placebo group (Group 2). The secondary outcome measures are key audiological and clinical assessments of hearing loss. OAE shift will be a secondary outcome measure and an early indicator of TTS and PTS.

Standard descriptive statistics will be used to describe distribution of demographic, clinical and audiometric characteristics as well as outcome measures for each study group. For continuous level characteristics Q-Q plots and Shapiro-Wilk test will be used to test assumption of normality. For normally distributed data mean and standard deviation will be used as descriptive stats of continuous level variables, and if the assumption of normality is violated we will report median and range for description of variables. Frequency and relative frequency will be used for description of categorical level variables.

## **12.2 Efficacy analysis**

### **12.2.1 Analysis of primary outcome variable**

#### **Efficacy analysis at the end of the study**

The primary outcome measure for assessing effectiveness of ZNS (100 mg PO) post-shooting compared to the placebo group will be the proportion of officers with TTS defined as PTS positive 30 days (+/- 3 days) after shooting range exposure.

Audiogram will be performed to look for PTS. Officers for whom the difference at any frequency from 2-6 kHz in hearing thresholds (30 days (+/- 3 days) post-shooting - Baseline) is  $\geq 10$  dB HL will be defined as PTS positive. Primary analysis and sensitivity analyses will be carried out on the primary endpoint.

#### **Primary analysis.**

Frequency and relative frequency will be used to describe the distribution of the primary outcome measure in each study group. To assess efficacy, Fisher's exact test will be used to compare the proportion of officers with PTS positive in ZNS group with the proportion of officers with PTS positive in the placebo group.

To provide an estimate of treatment effect a supportive logistic regression analysis will be done with covariates: age, pre-existing hearing loss dichotomized to normal to minimal hearing loss and slight to mild loss, noise exposure history dichotomized to high risk and low risk, average post-shooting

### Sensitivity analysis of the primary endpoint

The potential impact of missing primary endpoint data will be explored in sensitivity analyses using multiple imputation. Two sensitivity analyses performed:

Sensitivity 1: MI analysis under the missing not at random assumption (MNAR)

Sensitivity 2: Logistic regression tipping point analysis under the assumption of data missing at random.

#### Sensitivity 1.

Proc MI procedure in SAS will be used to impute missing data for study treatment groups using the distribution implied by the non-missing officer data within the placebo group. The SAS code to impute data for Sensitivity analysis 1 under the MNAR assumption will be of the form:

```
PROC MI DATA=X SEED=<value> NIMPUTE=10 OUT=MI_OUT1 NOPRINT;
  CLASS GROUP;
  VAR AGE PTA LSurg.....;
  FCS LOGISTIC(PTS);
  RUN;
```

Post imputation each of the imputed 10 datasets will be analyzed using the same approach as for the primary outcome measure. The estimates of the analysis of the 10 imputed datasets will be then combined following Rubin's rules using PROC MIANALYZE procedure in SAS which will be of the form:

```
PROC MIANALYZE PARMs=GMPARMS COVB=GMCOVB PARMINFO=GMPINFO WCOV
  BCOV
  TCOV; / *dataset "gmparms" contains the estimates and
  associated standard errors for the mean parameters from each of
  the M=10 imputed data sets.
  dataset "gmcovb" contains the asymptotic covariance matrices
  dataset "gmpinfo" contains parameter info*/
  MODELEFFECTS INTERCEPT AGE PTA LSurg.....;
  RUN;
```

#### Sensitivity 2.

Multiple imputation will be used to impute data in each of the study groups. A progressive penalty of  $\delta_i = k_i \times \log(OR)$  will be added to imputed

values in ZNS arm where (i)  $OR$  is the Odds ratio estimate for ZNS as compared to Placebo from the primary logistic regression analysis and (ii)  $k_i = 1, 0.95, 0.90, \dots, 0.05, 0, 1.05, 1.10, \dots$  thus  $k$  ranges from 1 (equivalent to MI approach based on MAR) to 0 (or higher), until the conclusion of the primary analysis is overturned (i.e.,  $p < 0.05$  is lost at, this value of  $k_i$  being the ‘tipping point’). Rubin’s method will be used to combine the primary endpoint treatment effects across imputations for each value,  $k_i$ , of the penalty. Forest plots will be used to graphically display the penalty value that results in loss of statistical significance.

SAS code sample for Sensitivity analysis is provided below:

```

**Step 1: Generate 10 datasets by imputing the missing data**;

PROC MI DATA=X SEED=<value> NIMPUTE=10 OUT=MI_OUT1 NOPRINT;
CLASS GROUP;
VAR AGE PTA LSurg.....;
FCS LOGISTIC(PTS);
RUN;

**Step 2: Generate 10 complete datasets from the 10 monotonized
datasets in Step 1 for missing values in the drug arm,
subtract DELTA derived above from their imputed data.**;
proc mi data=YYY NIMPUTE=1 SEED=<value> OUT=YYY_shift;
by group;
class group;
var AGE PTA LSurg.....;
monotone method=logistic;
mnar adjust(PTS / shift=DELTA adjustobs=(group='1'));
run;

**Step 3: Apply the primary MMRM to the 10 complete datasets in
Step 2**;
proc genmod data=YYY_shift descending;
by _imputation_;
class group;
model PTS = group AGE PTA LSurg.....;
ods output GEEModPEst=gmparms;
run;

**Step 4: Obtain the pooled inference from 10 sets of estimates
from Step 3**;

PROC MIANALYze PARMS=GMPARMS COVB=GMCovB PARMINFO=GMPINFO WCOV
BCOV
TCOV;
MODELEFFECTS group;
RUN;

```

## 12.2.2 Analysis for secondary outcome measures.

The focus of the study is to determine efficacy of ZNS for treatment of acute hearing loss based on the testing of the hypothesis for the primary outcome. In addition, we will also conduct analysis to evaluate other important audiologic measures. The secondary outcome measures are key audiological and clinical assessments of hearing loss, and include: Audiometric TTS, DPOAEs, Ultra-high frequency audiometry, ECochG, and WIN testing 30 days (+/- 3 days) after shooting, and are measured as continuous level variables. We do not plan any adjustment of alpha error for multiple comparisons.

Analysis of variance (ANCOVA) will be used for comparison of outcome measures between each of the ZNS groups and placebo study group after controlling for baseline value, age, pre-op hearing dichotomized to: normal to minimal hearing loss and slight to mild loss, noise exposure history dichotomized to: high risk and low risk, average post-shooting TTS.

Statistical analyses will be conducted using the SAS software (SAS Institute Inc., Cary, N.C., USA).

Measurements will include (1) the average audiogram threshold shift between 3 and 6 kHz (sensitive region for NIHL) and 10 and 16 kHz (markers for hidden hearing loss), (2) DPOAE amplitudes, (3) ECochG changes (AP amplitude and latency, AP width), and (4) WIN scores.

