#### **4.0 STUDY DESIGN**

A randomized, double-blind, and placebo-controlled clinical trial has been designed.

Study participants will be recruited from the Akron Police Department, Summit County Police Department, and other local surrounding police departments. Police officers will be offered participation if they are training for firearm certification as part of their standard occupational requirements. These are officers that would be recommended and/or required to complete these trainings/certifications despite this investigation and this investigation will have no influence on audiologic recommendations.

The primary efficacy endpoint will be the proportion of PTS-positive subjects defined as the ratio of PTS-positive subjects to total number of subjects within each study arm/group. Subjects defined as PTS-positive will demonstrate an increase in threshold that is  $\geq 10$  dB HL at any frequency from 2-6 kHz post-shooting as compared to baseline audiogram.

The secondary efficacy outcome measures will be: (1) the proportion of PTS-positive subjects as defined above, but the definition of PTS will also include the NIOSH red flag guideline for permanent threshold shift: an increase in hearing threshold level of 15 dB or more at any frequency (2, 3, 4, 6 kHz). (2) The rate of temporary cochlear change as measured by a DPOAE amplitude shift at any frequency that is significantly greater than the stability of each measurement (i.e., 95% confidence interval of each measurement do not overlap). The rate of DPOAE shift is the ratio of DPOAE shift-positive subjects to total subjects within each arm.

Interested police officers will be consented and enrolled in the study. They will then undergo screening for TTS following shooting range noise exposure. Those officers identified with TTS will be randomized via an interactive randomization tool (IRT) and assigned to a study group. Once assigned the subject will be provided a kit that will contain either ZNS (100 mg PO) or a placebo. The ZNS and placebo capsules will look, taste, and smell the same. Participants will be instructed to take zonisamide without food. We will recommend that capsules be swallowed whole per the current approved labeling. Those without TTS will be finished with their study commitment.

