3.2 Primary Efficacy Outcome

The primary efficacy outcome will be the proportion of PTS positive subjects defined as the ratio of PTS-positive subjects to total number of subjects in each study arm/group. PTS positive will be defined as all subjects who in audiogram are identified as having a permanent threshold shift (PTS) of ≥ 10 dB HL increase at any frequency from 2-6 kHz after shooting as compared to baseline audiogram. A SAS code will be written to code as PTS positive all the officers for whom the difference at any frequency from 2-6 kHz in hearing thresholds (30 days (+/- 3 days) post shooting - Baseline) will be ≥ 10 dB HL in at least one of the ears. If this difference is less than 10 dB then the officers will be coded as non-PTS positive.

To date, there are no reports of ZNS being associated with hearing damage or loss, so the hypothesis for this study will be a one-sided hypothesis.

For the primary outcome measure, the null and alternative hypotheses are provided below.

Comparison of the proportion of PTS-positive subjects between ZNS group and Placebo

$$H_0: p_{ZNS} - p_{Placebo} = 0 \quad H_A: p_{ZNS} < p_{Placebo}$$

We hypothesize that ZNS will reduce the proportion of PTS-positive officers by an absolute difference of 25% as compared to placebo. Our one-sided hypothesis is supported by animal studies, and lack of any evidence of hearing loss as a side effect of ZNS in human studies.

Hypothesis testing for the primary outcome will be performed at the one-sided alpha level of 0.025.

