3.3 Secondary efficacy outcomes

The study is designed to test the null hypothesis associated with the primary efficacy measure. Nevertheless, it provides a great opportunity to evaluate the impact of ZNS on other audiometric and clinical measures:

- DPOAEs: Distortion product otoacoustic emissions will be measured at baseline

(before shooting), as well as within 5-10 minutes after shooting and 30 days (+/-3 days) post-shooting (for officers with positive TTS) to measure both temporary and permanent changes in DPOAE amplitude relative to baseline. A change is noted in DPOAE amplitude at any frequency that is significantly greater than the stability of each measurement (i.e., 95% confidence interval of each measurement do not overlap).

- Ultra-high frequency audiometry: Ultra-high frequency audiometry (10-14 kHz) will be measured at baseline (before shooting), 30 days (+/-3 days) after shooting (for officers with positive TTS) to measure for both temporary and permanent high frequency audiometric changes. A significant change is defined for any frequency that is greater than 5 dB HL from baseline thresholds.
- ECochG: Electrocochleography will be measured at baseline (before shooting) and 30 days (+/-3 days) after shooting (for officers with positive TTS) to measure for changes in ECochG AP amplitude, latency and width.
- WIN testing: The Words-In-Noise test will be administered at baseline (before shooting) and 30 days (+/-3 days) after shooting (for officers with positive TTS). The respective scores will be converted to Z-scores to evaluate for any change in scores relative to baseline.

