Multiple imputation will be used to impute data in each of the study groups. A progressive penalty of $\delta_i = k_i \times \log(OR)$ will be added to imputed values in ZNS arm where (i) OR is the Odds ratio estimate for ZNS as compared to Placebo from the primary logistic regression analysis and (ii) $k_i = 1, 0.95, 0.90, \dots, 0.05, 0, 1.05, 1.10, \dots$ thus k ranges from 1 (equivalent to MI approach based on MAR) to 0 (or higher), until the conclusion of the primary analysis is overturned (i.e., $p < 0.05$ is lost at, this value of k_i being the 'tipping point'). Rubin's method will be used to combine the primary endpoint treatment effects across imputations for each value, k_i , of the penalty. Forest plots will be used to graphically display the penalty value that results in loss of statistical significance.

SAS code sample for Sensitivity analysis is provided below:

```
**Step 1: Generate 10 datasets by imputing the missing data**;

PROC MI DATA=X SEED=<value> NIMPUTE=10 OUT=MI_OUT1 NOPRINT;
CLASS GROUP;
VAR AGE PTA LSurg....;
FCS LOGISTIC(PTS);
RUN;

**Step 2: Generate 10 complete datasets from the 10 monotonized datasets in Step 1 for
missing values in the drug arm,
subtract DELTA derived above from their imputed data.**;
proc mi data=YYY NIMPUTE=1 SEED=<value> OUT=YYY_shift;
by group;
class group;
var AGE PTA LSurg....;
monotone method=logistic;
mnar adjust(PTS / shift=DELTA adjustobs=(group='1'));
run;

**Step 3: Apply the primary MMRM to the 10 complete datasets in Step 2**;
proc genmod data=YYY_shift descending;
```

```
by _imputation_;
class group;
model PTS = group AGE PTA LSurg.....;
ods output GEEModPEst=gmparms;
run;

**Step 4: Obtain the pooled inference from 10 sets of estimates from Step 3**;

PROC MIANALYze PARMS=GMPARMS COVB=GMCOVb PARMINFO=GMPINFO WCOV BCOV
TCOV;
MODELEFFECTS group;
RUN;
```

7.1.2 Analysis for secondary outcome measures.

The focus of the study is to determine efficacy of ZNS for treatment of acute hearing loss based on the testing of the hypothesis for the primary outcome. In addition, we will also conduct analysis to evaluate other important audiologic measures. The secondary outcome measures are key audiological and clinical assessments of hearing loss, and include: Audiometric TTS, DPOAEs, Ultra-high frequency audiometry, ECochG, and WIN testing 30 days (+/- 3 days) after shooting, and are measured as continuous level variables. We do not plan any adjustment of alpha error for multiple comparisons.

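### Secondary endpoint 1, as worded in Protocol 4.0, equals the primary endpoint and is absent from the SAP; the DPOAE shift rate has no named between-group test and is tied to a time at or before dosing

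*Protocol*

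**What the plan says.** **Primary endpoint.** Protocol 4.0 and 12.2.1 count an officer as PTS-positive on a rise of at least 10 dB at any frequency from 2 to 6 kHz. SAP 3.2 has the same rule ("dB HL increase at any frequency from 2-6 kHz after shooting as compared to baseline audiogram") and adds that one ear is enough.

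**Secondary outcome 1, Protocol 4.0.** This is the proportion PTS-positive under the primary rule, except that "the definition of PTS will also include the NIOSH red flag guideline for permanent threshold shift". The guideline is given as a rise of 15 dB or more at 2, 3, 4 or 6 kHz.

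**Secondary outcome 2, Protocol 4.0.** This is a rate of temporary cochlear change based on DPOAE amplitude: "The rate of DPOAE shift is the ratio of DPOAE shift-positive subjects to total subjects within each arm".

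**Analysis sections.** Protocol 12.2.2 lists audiometric TTS, DPOAEs, ultra-high frequency audiometry, ECochG and WIN. It says that they "are measured as continuous level variables" and that "Analysis of variance (ANCOVA) will be used for comparison of outcome measures". SAP 7.1.2 carries the same list, the same scale ("and are measured as continuous level variables") and the same method. Neither section mentions the 15 dB criterion or a DPOAE rate.

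**SAP definitions and outputs.** SAP 3.3 lists DPOAEs, ultra-high frequency audiometry, ECochG and WIN. For DPOAE it keeps a yes/no criterion ("A change is noted in DPOAE amplitude at any frequency that is significantly greater than the stability of each measurement") but attaches no per-arm rate and no test. The table index in SAP 12.1 has DPOAE tables of actual values and change from baseline, and none for a 15 dB endpoint or a shift rate.

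**The concern.** The protocol's design section and the sections that govern the analysis describe different secondary endpoints. A programmer who follows Protocol 4.0 to the letter would produce a first secondary endpoint with the same count as the primary. One who follows the SAP would produce no such endpoint. For DPOAE, the endpoint is a proportion in one place and a continuous amplitude in the other.

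At stake is prespecification. The 15 dB criterion was added by amendment and is useful only as a stricter check on PTS. No alpha adjustment is planned for the secondaries. If the definition and test stay open, the choice between the combined rule, 15 dB alone and a continuous shift could be made after the data are seen.

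**Working it through.** **1. Does the 15 dB criterion change the count?** Let A be the officers with a rise of at least 10 dB at any frequency from 2 to 6 kHz, and B those with a rise of at least 15 dB at 2, 3, 4 or 6 kHz. A rise of at least 15 dB is a rise of at least 10 dB, and the four frequencies lie within 2 to 6 kHz. So B is a subset of A, and A ∪ B = A. This needs no assumption about rates.

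Enumeration agrees. Take shifts from −10 to +30 dB in 5 dB steps (the step is an assumption), which gives 9 values at 4 frequencies:

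- All profiles: 9⁴ = 6,561.
- Profiles where A ∪ B differs from A: 0.
- Profiles where B alone differs from A, meaning the largest shift is exactly 10 dB: 5⁴ − 4⁴ = 625 − 256 = 369.

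The 369 is a count of patterns, not a probability. It shows that only the reading of 15 dB alone gives a separate endpoint.

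**2. Which test applies to each proportion?**

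| Endpoint | Protocol 4.0 | Protocol 12.2.2 / SAP 7.1.2 | SAP 3.3 | SAP 12.1 |
|---|---|---|---|---|
| 15 dB criterion | proportion | absent | absent | no table |
| DPOAE shift | proportion | continuous, ANCOVA | yes/no criterion, no rate | actual and change only |

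Fisher's exact test is assigned to the primary endpoint only (Protocol 12.2.1, SAP 7.1.1).

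**3. When is the DPOAE shift measured?** Protocol 5.4 and the study calendar place the immediate DPOAE at Visit 3, together with the audiogram that looks for TTS. The calendar and SAP 2.5 say that study drug is dispensed after TTS is identified on that audiogram. A shift recorded before the dose cannot show a drug effect. The documents do not state the order of DPOAE and dosing within Visit 3, but both follow directly on the shooting. The next DPOAE is at Visit 5, 30 days (±3) after training.

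**4. What power would a separate 15 dB endpoint have?** First, the plan's own primary figure: n = 66 per arm, 50% against 25%, one-sided α = 0.025, stated power 80.5%. The continuity-corrected arcsine approximation for Fisher's test is

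Φ{√(2n)·[asin√(p₁ − 1/2n) − asin√(p₂ + 1/2n)] − 1.96} = Φ{11.489 × (0.7778 − 0.5323) − 1.96} = Φ(0.861) = 80.5%.

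Full enumeration sums the binomial probabilities of all outcome pairs whose one-sided hypergeometric p-value is at most 0.025, and gives 81.3%. The plan's figure is reproduced.

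The documents give no rate for a 15 dB rise. By the subset argument it cannot exceed the primary rate, assumed to be 50% on placebo. **Assuming** the placebo rates below, halved by treatment, with 66 per arm and one-sided α = 0.025:

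| Placebo / ZNS rate | Fisher's exact power | Pooled z-test power |
|---|---|---|
| 10% / 5% | 10% | 19% |
| 20% / 10% | 28% | 36% |
| 30% / 15% | 47% | 54% |
| 40% / 20% | 65% | 71% |
| 50% / 25% (upper bound) | 81% | 85% |

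**The case against.** The strongest reply is that the intent is clear. The protocol's revision history describes the NIOSH criterion as added as a secondary endpoint, and Protocol 4.0 numbers it separately, so 15 dB alone was probably meant. That stands as a reading of intent, and it means the wording does not prove that a duplicate would be reported. It does not change the current text, and under either reading the SAP omits the endpoint.

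A reader might infer that endpoint 1 both duplicates the primary and lacks a valid test. The two cannot hold together. If the combined rule is meant, Fisher's exact test on the primary already tests it. If 15 dB alone is meant, it is a different endpoint that lacks a named test.

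A reader might also infer that the plan applies ANCOVA to yes/no data. The statement about scale follows a list that does not contain the 15 dB proportion, and Protocol 12.2.2 names DPOAE amplitudes as the variable. That sentence is correct for those measures. The fault is an omission: no method is given for the proportions.

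Finally, the secondary objectives (Protocol 2.2, SAP 2.2.2) do not name the 15 dB criterion, so deleting it from Protocol 4.0 would also reconcile the documents. That is a fair alternative, at the price of the stricter check.

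**Conclusion.** The point holds as a fault of definition and consistency in the secondary endpoints. Read literally, secondary endpoint 1 adds 0 officers to the primary count, and it is absent from SAP 3.3, 7.1.2 and 12.1. The DPOAE shift rate has no named between-group test, and its description as temporary ties it to a measurement taken at or before dosing.

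The primary endpoint, its test and its sample size are unaffected. It would be too strong to say that the stricter check is lost. Protocol 12.1 and SAP 5.1 plan frequencies for categorical variables, and the SAP tabulates and lists audiogram thresholds, so a 15 dB count could still be derived and described. What is missing is a prespecified definition and comparison.

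The identity with the primary rests only on reading the combined definition literally. The power range of about 10% to 65% rests on assumed placebo rates of 10% to 40%, halved by treatment. The timing point rests on the Visit 3 sequence in the calendar and SAP 2.5.

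**What to change.** 1. **15 dB endpoint.** In Protocol 4.0, define secondary endpoint 1 as a rise of 15 dB or more, in place of 10 dB, at 2, 3, 4 or 6 kHz in at least one ear at Visit 5. Add it to SAP 3.3, 7.1.2 and the table index in 12.1, and compare the arms by Fisher's exact test as for the primary. State that power for it is not established, because the documents give no rate.
2. **DPOAE.** In Protocol 4.0, replace the temporary shift rate with Visit 5 DPOAE amplitude change, analysed by the planned ANCOVA. If the rate is kept, define it at Visit 5, test it with Fisher's exact test and add a table for it. Align the note in Protocol 3.2, which calls DPOAE a secondary measure of TTS.

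The cost is wording in the protocol and SAP and one or two more table shells. The audiogram and DPOAE are already scheduled at baseline and Visit 5, so no new data are needed. The change should be made before unblinding.
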